8.1.2.2 Attribution Definitions

An AE is considered to be associated with the use of the study treatment if the attribution is determined as possible, probable or definite. Attribution of AEs will be recorded in the CRF as:

- Unrelated: The AE is clearly *not* related to the study treatment.
- Unlikely: The AE is doubtfully related to the study treatment.
- Possible: The AE may be related to the study treatment.
- Probable: The AE is likely related to the study treatment.
- Definite: The AE is clearly related to the study treatment.

8.1.2.3 Definition of an Unexpected Adverse Event

An unexpected AE is defined as any adverse drug experience, the specificity or severity of which is not consistent with the current Investigator Brochure; or, if an Investigator Brochure is not available, the specificity or severity of which is not consistent with the risk information described in this protocol or in the regulatory agency study authorization application.

For study treatments used in this protocol that have been approved for use in the US by the FDA (i.e., venetoclax, and azacitidine), the reference safety information that will be used for making expectedness decisions is the most current version of the product USPI that can be found on the FDA website.

Unexpected, as used in this definition, refers to an adverse drug experience that has not been previously observed (e.g., included in the Investigator's Brochure or USPI, as applicable) rather than from the perspective of such experience not being anticipated from the pharmacological properties of the pharmaceutical product.

8.1.2.4 Serious Adverse Event (SAE)

A serious adverse event is defined as any untoward medical occurrence that at any dose:

1. Results in death,
2. Is life-threatening (i.e., the patient was at risk of death at the time of the event. It does not refer to an event which hypothetically might have caused death if it was more severe),
3. Requires in-patient hospitalization or prolongation of existing hospitalization excluding that for pain management, disease staging/re-staging procedures, or catheter placement unless associated with other serious events,
4. Results in persistent or significant disability/incapacity, or
5. Is a congenital anomaly/birth defect.

Important medical events that may not result in death, be life-threatening, or require hospitalization may be considered serious adverse drug events when, based on appropriate medical judgment, they may jeopardize the patient and may require medical or surgical intervention to prevent one of the outcomes listed above.

8.1.2.5 Pregnancy

Any pregnancy detected during the study, or that occurs within 30 days after stopping study medication, must be reported immediately to the Investigator. Pregnancy, in and of itself, is not regarded as an AE, unless there is suspicion that study medication may have interfered with the effectiveness of a contraceptive medication. If the patient becomes pregnant while on-study, the study drug should be immediately discontinued. Pregnancy information about a female patient or a female partner of a male patient should be reported immediately from the time the Investigator first becomes aware of a pregnancy or its outcome. This will be performed by the Investigator per instructions from the Sponsor's monitoring CRO.

Any pregnancy complication, spontaneous abortion, elective termination of a pregnancy for medical reasons, outcome of stillbirth, congenital anomaly/birth defect, or serious adverse event in the mother will be recorded as an SAE and will be reported as described in Section [8.1.2.6](#).

8.1.2.6 Reporting of Serious Adverse Events

AEs classified as serious require expeditious handling and reporting to Sponsor's monitoring CRO to comply with regulatory requirements.

For any serious adverse event (SAE) that occurs while a patient is on-study; within 30 days of the last study treatment administration, regardless of any opinion as to the relationship of the SAE to the study treatment; or if any SAE that the Investigator feels is related to the study treatment occurs later than 30 days after the last study treatment administration, the Sponsor's monitoring CRO must be notified immediately (within 24 hours of becoming aware of the event) by electronic data capture (EDC) system, email, fax or telephone. Notification by email is preferred. The primary mechanism for reporting an SAE to the sponsor will be the electronic data collection tool. An SAE eCRF should be completed in the electronic data capture (EDC) system within 24 hours of site becoming aware of the event. EDC Alerts will be sent to Safety desk for all SAEs.

If the EDC system is inaccessible/unavailable, then the site will use the paper SAE form in order to report the SAE within 24 hours. Emailing the paper SAE forms is the preferred method of notification.

SAEs will be reported to: Email: [REDACTED]

8.1.2.7 Safety Monitoring Plan

The medical monitor is responsible for ongoing safety monitoring for the study per the detailed safety plan. This monitoring will include a review of all serious AEs as they are reported by the study site. The medical monitor will also be in contact with site monitors and will be available to discuss any issues concerning safety with site staff. Safety data will be reviewed periodically by [REDACTED] and the Sponsor Medical Officer.

DRT consisting of the Medical Monitor, Site Principal Investigators, and other clinical research personnel that the Sponsor may deem appropriate, will hold DRM on an interim basis at a frequency dependent on study accrual. At these meetings, the DRT will review AEs and DLTs and make recommendations regarding the RP2D. In the expansion portion of the study, the DRT will evaluate safety and tolerability after 5 patients have completed 1 cycle of treatment in each cohort. All accumulated safety data will be discussed during DRMs.

The DRT will produce summaries or minutes of these meetings. These summaries will be available for inspection when requested by any of the regulatory bodies charged with the safety of human subjects and the integrity of data.

8.2 Efficacy Assessments

8.2.1 Complete Remission Rate

CR rate will be defined as the proportion of patients who achieve CR.

8.2.2 Duration of Response

DoR will be measured from the time of initial response to disease relapse/progression or death.

8.2.3 Overall Response Rate

Overall response rate (ORR) will be defined as the proportion of patients achieving CR, CRI, complete remission with CRp, partial remission (PR) and MLFS by the IWG 2003 AML criteria ([APPENDIX I](#)).

8.2.4 Overall Survival

Overall survival (OS) is defined for all enrolled patients, as measured from the date of enrollment until the date of death.

8.2.5 Stem Cell Transplant

Patients may go on to receive SCT and this is likely to be a reflection of a positive outcome to treatment. The primary approach will be to use a treatment policy strategy (ICH E9 (R1) addendum) where patients who receive SCT will continue to be followed for OS and relapse from any response with their date of death/relapse used in the analysis. If for any reason a patient receives SCT prior to a documented CR they will not be counted as a response. Sensitivity analyses may be performed as counting post-SCT CR/PR as a response.

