- q. Please consult Section [8.4](#) for PK collection schedule.
- r. Patients discontinuing treatment should complete their end of treatment visit within approximately 28 days of their last dose of APR-246. Physical exam, vital signs, clinical toxicity assessment, hematology, serum chemistry and bone marrow aspirate and biopsy with NGS analysis should be performed, if feasible.
- s. Long-term follow up can be done remotely (e.g. via telephone, via local practitioner or via review of medical records). Assuming there is no withdrawal of consent, patients who stop study treatment for any reason (e.g. toxicity, transition to SCT, PD) will continue long-term follow-up (see Section [7.4](#)). If a patient is removed from the study due to unacceptable AEs, the event(s) will be followed until resolution or stabilization of the AE. Off-treatment data on overall survival will be updated every month (i.e. every 28 days \pm 3 days) or until death or withdrawal of consent for study participation, whichever occurs first. If a patient is removed from the study due to unacceptable adverse events (AEs), the event(s) will be followed until resolution or stabilization of the adverse event. Patients who respond and discontinue study treatment for reasons other than PD should have response assessments and survival should be collected every month until relapse, death or withdrawal of consent for study participation, whichever occurs first. After relapse, data for

survival should be collected every month (i.e. every 28 days ± 3 days) until death or withdrawal of consent for study participation, whichever occurs first.

- t. AE description, grade and start date and resolution date should be documented.

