8.3 Progression-Free Survival (PFS)

Progression-free survival (PFS) is defined for each patient as the time from start of treatment to the date of the first documented progression or death due to any cause. Patients who die without a reported prior progression will be considered to have progressed on the date of their death. Patients who did not progress or die will be censored on the date of their last evaluable tumor assessment. Patients who started any subsequent therapy without a prior reported progression will be censored at the last evaluable tumor assessment prior to the initiation of the subsequent anticancer therapy.

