9.5 Efficacy

CR will be summarized for all enrolled patients as the proportion of patients (%) with CR. In addition to presenting the CR rate, its associated exact 95% CI for each treatment arm will also be presented. CR rate will not be formally compared between treatment arms.

DoR will be defined as the time from the date when criteria for response are met to the date of PD or death due to any cause, whichever occurs first. Patients that are alive without relapse or progression will have their DOR censored at the date of the last clinical assessment. The duration of CR will be summarized in each treatment arm by providing DOCR and DOR, using Kaplan-Meier methodology. DoR endpoints will not be formally compared between treatment arms.

Overall response will be summarized in number (%) of patients in each category of responses and ORR will be analyzed by using the similar method as CR rate.

Survival data will be collected at treatment and follow-up periods. Patients will be followed until death, or withdrawal of consent for study participation. OS is defined as the number of days from the date of enrollment to the date of death. Kaplan-Meier methodology will be utilized.

PFS will be defined as the time from the date of enrollment to disease progression or death from AML whichever occurs first. If neither event occurs, PFS will be censored at the date of the last assessment. Kaplan-Meier methodology will be utilized.

Transition rate to SCT will be analyzed using the similar methods as CR.

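### PFS has two unreconciled censoring rules; read literally, the one in Section 8.3 censors patients at transplant, unlike the treatment-policy approach that 8.2.5 makes primary for SCT

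*Combined protocol and SAP*

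**What the plan says.** **PFS, Section 8.3.** "Patients who started any subsequent therapy without a prior reported progression will be censored at the last evaluable tumor assessment". The assessment meant is the last one before the new therapy begins. The sentence starts with any subsequent therapy and ends with subsequent anticancer therapy. Neither term is defined in relation to SCT or its conditioning.

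**PFS, Section 9.5 and the synopsis (efficacy analyses).** A patient with no event is censored at the last assessment (the synopsis says last clinical assessment). Neither place has a subsequent-therapy rule. The endpoint list in 9.3.2 gives no PFS censoring rule at all.

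**SCT, Section 8.2.5.** Treatment policy is the primary approach: "patients who receive SCT will continue to be followed for OS and relapse from any response", and their death or relapse dates are used. OS and relapse are named; PFS is not. The same section says: "If for any reason a patient receives SCT prior to a documented CR they will not be counted as a response".

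**Duration of response, Sections 8.2.2 and 9.5.** Section 8.2.2 defines it: "DoR will be measured from the time of initial response to disease relapse/progression or death". Section 9.5 gives the censoring rule: "Patients that are alive without relapse or progression will have their DOR censored at the date of the last clinical assessment". There is no censoring at SCT or at new therapy.

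**Follow-up, Section 7.1, footnote s.** "patients who stop study treatment for any reason (e.g. toxicity, transition to SCT, PD) will continue long-term follow-up". Footnote s and Section 7.4 schedule monthly response assessments for responders who stop treatment for reasons other than progression.

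**The concern.** Two analysts working from this plan could produce different PFS curves, and both would be following the text. One applies 8.3 and stops the clock before transplant. The other applies 9.5 and carries the patient through transplant. The trial is open-label and transition to transplant is itself a secondary endpoint, so the event is expected. The choice between rules could be made after the outcomes of transplanted patients are known.

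The literal reading of 8.3 is a natural one. Tables 1 and 3 list SCT among the prior therapies, beside venetoclax, hypomethylating agents and intensive chemotherapy, and footnote s treats transition to SCT as a reason for stopping study treatment. Under that reading, patients transplanted without progression are censored. Section 8.2.5 describes SCT as probably reflecting a good result of treatment, so these patients are unlikely to be a random sample of those still at risk. Kaplan-Meier would nevertheless give them the later risk of the patients who were not transplanted.

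**Working it through.** **1. One patient under each rule.** Take a patient with CR documented before transplant, SCT at month 4 without progression, and death from AML at month 12 (an event under every definition in the plan).

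| Analysis | Result for this patient |
|---|---|
| PFS, 9.5 and synopsis | event at month 12 |
| PFS, 8.3 read literally | censored at the last evaluable assessment before month 4 |
| Duration of response, 8.2.2 and 9.5 | event at month 12 |
| OS, 8.2.5 | event at month 12 |

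The two PFS rows disagree. This is the firm inconsistency, and it does not depend on 8.2.5.

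**2. Is there a plan figure to reproduce?** Not for PFS: no power, event count or test is stated. The only powered figure is the Simon design for response in cohorts 2 and 5 (Section 9.1). It reproduces, with exact type I error 0.0458 and power 0.801, and is unaffected by this point.

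**3. Size, closed form.** All inputs are assumptions. A share *s* of patients is transplanted at month 4 while event-free. Median PFS without SCT is 5 months, and the post-SCT median is *m*. With h1 = ln2/5 and h2 = ln2/m:

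- Treatment policy: PFS(12) = (1−s)·exp(−12·h1) + s·exp(−8·h2)
- Censored at SCT: PFS(12) = [(1−s)·exp(−4·h1) + s]·exp(−8·h1)
- Treatment policy minus censored = s·[exp(−8·h2) − exp(−8·h1)]

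The constants are exp(−12·h1) = 0.1895, exp(−4·h1) = 0.5743 and exp(−8·h1) = 0.3299.

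| s | Post-SCT hazard | exp(−8·h2) | Treatment policy | Censored | Difference (points) |
|---|---|---|---|---|---|
| 10% | m = 6 | 0.3969 | 21.0% | 20.4% | 0.7 |
| 20% | m = 12 | 0.6300 | 27.8% | 21.8% | 6.0 |
| 30% | m = 24 | 0.7937 | 37.1% | 23.2% | 13.9 |
| any | unchanged (m = 5) | 0.3299 | equal | equal | 0 |
| 30% | ratio 1.5 | 0.1895 | 18.9% | 23.2% | −4.2 |

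Differences are taken before rounding. For the last row: 0.3 × (0.1895 − 0.3299) = −0.042.

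**4. Size, simulation.** Again all inputs are assumed: 400,000 patients per scenario, exponential PFS with median 6 or 8 months without SCT, SCT between months 3 and 6, 6% to 27% transplanted while event-free, post-SCT hazard ratio 0.25 to 1.5, and 24 months of follow-up.

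- 6-month case, 12-month PFS: about 25% censored against 22% to 34% under treatment policy.
- 8-month case, 12-month PFS: about 35% censored against 32% to 44%.
- Median PFS: censoring is lower by up to about 1.7 months (8.01 against 9.76) if SCT lowers the hazard, and higher by up to about 0.6 months (7.97 against 7.42) if SCT raises it.
- Hazard ratio 1: no difference.
- PFS events lost to censoring per 33 patients: about 1 to 8.

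**The case against.** A reader might infer that 8.3 flatly contradicts 8.2.5. The text does not support that. Section 8.2.5 names OS and relapse from response, PFS has its own section, and a trial may handle one intercurrent event differently for different endpoints. If SCT is not meant as subsequent anticancer therapy, 8.3 and 8.2.5 agree, although the plan never says so. What stands is that 8.3 and 9.5 differ within PFS itself.

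A reader might also infer that transplanted patients drop out of PFS but always stay in duration of response. Neither half holds as stated. They are censored early, not excluded, and only if they had not progressed. The contrast with duration of response applies only to patients whose response counts. On the literal wording of 8.2.5, a patient transplanted before a documented CR is not a responder.

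Nor can every transplant death missing from PFS be blamed on this censoring. Section 9.5 and the synopsis count only deaths from AML, while 8.3 counts deaths from any cause. That is a separate inconsistency, and it would remove non-AML transplant deaths under 9.5 with no SCT rule at all.

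On size, the inputs are assumed and the smallest favourable case is under 1 point. With 33 patients and 12-month PFS near 25%, the 95% half-width is about 1.96·√(0.25 × 0.75/33) = 15 points, wider than the central 6-point difference. The difference is nonetheless systematic, and a larger cohort would not remove it.

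Finally, treatment policy for PFS is a choice of estimand. That is true, but it is the strategy the plan already names as primary for SCT.

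**Conclusion.** The point holds in this form: the plan has two PFS censoring rules that give different results for the same transplanted patient. The 8.3 rule, read literally, departs from the approach that 8.2.5 sets for SCT and that duration of response follows.

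The direction of any bias is not known in advance. Under the stated assumptions, the 12-month difference is zero if SCT leaves the hazard unchanged. Censoring gives roughly 6 to 14 points less in the central and most favourable closed-form cases, less than 1 point in the mildest, and up to 9 points less in the simulation. It gives about 4 points more if the post-SCT hazard ratio is 1.5. None of these is an estimate for this trial, because the documents state neither an SCT rate nor a post-SCT hazard.

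PFS is secondary and descriptive, and no test or decision rule rests on it. Severity is low to moderate.

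**What to change.** Put one PFS censoring rule, in the same words, in 8.3, 9.5 and the synopsis:

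- SCT and its conditioning are not subsequent anticancer therapy for this rule.
- The main PFS analysis follows the 8.2.5 treatment policy and uses the actual dates of progression or death after SCT.
- PFS censored at the last evaluable assessment before SCT is reported as a sensitivity analysis.
- For other subsequent anticancer therapy, either keep the 8.3 censoring or drop it, but do so identically in all three places.

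The cost is a few sentences and one extra run. There is one real limitation. Monthly response assessment after stopping treatment is scheduled only for responders. Non-responders transplanted without progression have only survival follow-up scheduled, so their post-SCT progression dates may be incomplete. The report should say so and give the number of such patients.

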8.3 Progression-Free Survival (PFS)

Progression-free survival (PFS) is defined for each patient as the time from start of treatment to the date of the first documented progression or death due to any cause. Patients who die without a reported prior progression will be considered to have progressed on the date of their death. Patients who did not progress or die will be censored on the date of their last evaluable tumor assessment. Patients who started any subsequent therapy without a prior reported progression will be censored at the last evaluable tumor assessment prior to the initiation of the subsequent anticancer therapy.

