- k. Initial response assessment (blasts percentage) is performed on Day 22 (± 3 days). In patients with bone marrow hypocellularity, venetoclax may need to be held and restarted after recovery of blood counts (ANC $\geq 0.5 \times 10^9/L$, and platelets $\geq 25 \times 10^9/L$), confirmed by repeat bone marrow biopsy on approximately Day 35 and following discussion with Medical Monitor. For subjects who

require a delay in study treatment for peripheral blood count recovery after a bone marrow evaluation, hematology values for up to 4 weeks from the bone marrow analysis can be used to determine the IWG response. Ongoing response assessments should be performed at the end of each cycle (every 4 weeks) starting at Cycle 2, based on peripheral blood and bone marrow sample (at the end of even cycles), and peripheral blood sample alone (at the end of odd cycles). After the first year of the study treatment response assessment will be performed every two months. Following a documented CR, a bone marrow aspirate/biopsy is not required if the response assessment can be made based on the peripheral blood, except at the time of suspected relapse at which time a bone marrow aspirate/biopsy is required.

- I. Hematology, including complete blood count with white blood cell differential, weekly. Additional peripheral blood sample should be collected on Day 1 of each cycle starting at Cycle 2 for disease assessment, if bone marrow aspirate is not available.
- m. Serum chemistry, including sodium, potassium, chloride, magnesium, CO₂, blood urea nitrogen (BUN), creatinine, glucose, calcium, albumin, total protein, total bilirubin, AST, ALT, alkaline phosphatase weekly. At screening, the creatinine clearance may be calculated from the serum creatinine. A 24-hour urine for creatinine clearance may be performed at Investigator's discretion.
- n. Serum or urine β hCG must be performed within 7 days prior to study treatment initiation in female patients of childbearing potential.
- o. Standard 12-lead ECGs in triplicate at screening, on Days 1–4 of Cycle 1 and on Days 1 of each subsequent cycle with patient in a semi-recumbent position. Please consult [Table 12](#) for ECG collection schedule.
- p. *Only in cohorts with venetoclax:* Potassium, phosphorus, calcium and uric acid should be evaluated approximately 6–8 hr and 24 hr (\pm 4 hr) after the initial administration of venetoclax in order to monitor for potential development of TLS.

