9.3.2 Secondary

1. CR rate, defined as the proportion of patients who achieve CR.
2. CR + CRi rate, defined as the proportion of patients who achieve CR or CRi.
3. CR + CRh rate, defined as the proportion of patients who achieve CR or CRh.
4. ORR, defined as the proportion of patients achieving CR, CRi, CRp, PR and MLFS by the IWG 2003 AML criteria ([APPENDIX I](#)). The CRh rate will also be determined and is defined as bone marrow blasts $<5\%$, ANC $>0.5 \times 10^9/L$ and platelets $>50 \times 10^9/L$.
5. OS, measured from the date of initiating study treatment to the date of death. Patients who have not died by the analysis data cut-off date will be censored at their last date of contact.

6. Rate of RBC and/or platelet TI for at least 56 days
7. PFS, defined from the date of initiating study treatment to the date of disease progression per IWG 2003 AML criteria ([APPENDIX I](#)) or death as a result of any cause.
8. Proportion of patients who transition to HSCT.
9. Pharmacokinetic parameters: C_{max} , AUC, V_d and CL of APR-246 and T_{max} , C_{max} and AUC of venetoclax.

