
APPENDIX I – Response Criteria Based on Modified Recommendations of the International Working Group for Diagnosis, Standardization of Response Criteria, Treatment Outcomes, and Reporting Standards in Acute Myeloid Leukemia⁵⁹

Response Criterion	Neutrophils, ×10 ⁹ /L	Platelets, ×10 ⁹ /L	Bone Marrow Aspirate Blasts (%) (by biopsy acceptable if aspirate not available)
CR	>1.0	>100	<5
CRI	ANC ≥1,000 OR platelets ≥100,000		<5
MLFS	NA	NA	<5
PR	>1.0	>100	>50% decrease from baseline to level of 5-25%
SD (for patients without a prior best response of CR, CRI, MLFS, or PR)	Absence of CR, CRI, PR, MLFS; and criteria for PD not met		
Hematologic relapse (for patients with a prior best response of CR, CRI, MLFS)	Bone marrow blasts ≥5%, or reappearance of blasts in the blood, on two consecutive assessments separated by ≥28 days. Development of new extramedullary disease.		
PD (for patients with a prior best response of SD or PR)	
Evidence for an increase in bone marrow blast percentage and/or increase of absolute blast counts in the blood, on two consecutive assessments at least 28 days apart:
 
>50% increase in marrow blasts over baseline (a minimum 15% point increase is required in cases with <30% blasts at baseline; or persistent marrow blast percentage of >70% over at least 3 months; without at least a 100% improvement in ANC to an absolute level ($>0.5 \times 10^9/L$ [500/mL], and/or platelet count to $>50 \times 10^9/L$ [50,000/mL] non-transfused); or
 
>50% increase in peripheral blasts (WBC × % blasts) to $>25 \times 10^9/L$ ($>25,000/mL$) (in the absence of differentiation syndrome); or
 
New extramedullary disease
		

Additional Responses to be Assessed in Addition to Above Responses
 
These responses in addition to other responses and do not have specific hematologic criteria.
			
Cytogenetic CR	Normal karyotype in a patient with abnormal cytogenetics at baseline.		

TP53 Molecular CR	TP53 mutation not detected by NGS based on local testing in a patient with detectable TP53 VAF by NGS at baseline.

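### PFS in 8.3: a patient who starts new therapy after a first, unconfirmed blast rise can be censored on the date of that rise, which biases PFS upward; 9.5 and the synopsis give a conflicting rule

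*Combined protocol and SAP*

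**What the plan says.** **PFS event.** Section 8.3 runs PFS to "the date of the first documented progression or death due to any cause". Section 9.3.2 ties progression to the response criteria: "PFS, defined from the date of initiating study treatment to the date of disease progression per IWG 2003 AML criteria", with a pointer to Appendix I.

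**Confirmation.** In Appendix I, the PD row (best response SD or PR) asks for the blast increase "on two consecutive assessments at least 28 days apart". The relapse row (best response CR, CRi or MLFS) asks for marrow blasts of at least 5%, "or reappearance of blasts in the blood, on two consecutive assessments separated by ≥28 days". New extramedullary disease stands in the relapse row without confirmation wording of its own.

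**PFS censoring and death in 8.3.** "Patients who started any subsequent therapy without a prior reported progression will be censored at the last evaluable tumor assessment", namely the one preceding the new therapy. Also: "Patients who die without a reported prior progression will be considered to have progressed on the date of their death".

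**PFS in 9.5 and the synopsis statistics.** A patient with neither progression nor death from AML is censored at the last assessment. New therapy is not mentioned.

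**DoR.** Section 9.5: "Patients that are alive without relapse or progression will have their DOR censored at the date of the last clinical assessment". Neither this sentence, nor 8.2.2, nor the synopsis censors DoR at new therapy. Section 8.2.5 applies a treatment-policy strategy to transplant for relapse and OS.

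**Follow-up.** New treatment for the disease ends study treatment (5.6.1). Responders who stop for reasons other than PD have monthly response assessments until relapse or death (7.4).

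**The concern.** Read together, these rules leave a gap between a first qualifying rise and its confirmation. During that time the patient has no Appendix I progression. If new therapy starts then, 8.3 looks back to the last evaluable assessment, which can be the one that showed the rise, and censors the patient there as progression-free.

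Kaplan-Meier removes a censored patient from the risk set and assumes that the patient's later hazard is like that of those who remain. Here censoring is triggered by the event itself, so the assumption fails in a known direction: true progressions leave the event count and estimated PFS rises.

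PFS is a named secondary endpoint in small, uncontrolled cohorts, where a few such patients can move a median. No stated sensitivity analysis counts an unconfirmed rise or new therapy as an event.

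**Working it through.** **1. The plan's own figures.** None is given for PFS or DoR. The only powered calculation is the Simon design for response in expansion cohorts 2 and 5. It reproduces (more than 4 of 18, then 11 or more of 33: exact alpha 0.046, power 0.801) and does not bear on this point.

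**2. One patient traced through the rules.** A first qualifying rise is seen on day 0, the earliest confirmation is day 28, and new therapy starts in between. For a responder, I read progression as the Appendix I relapse row.

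| Reading | PFS outcome |
|---|---|
| 8.3, single rise not reportable, new-therapy rule prevails | censored on day 0 |
| 8.3, single rise reportable as progression | event on day 0 |
| 8.3, patient later dies, death rule prevails | event on the date of death |
| 9.5 and synopsis | not censored at the switch; event at a later confirmed progression or AML death, otherwise censored at the last assessment |

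The first reading follows from the strict wording and is the only one that censors on the date of the rise. The third and fourth give an event that is late or missing. Only the second gives no upward shift.

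**3. Whether confirmation is likely to be obtained.** By footnote k of the study calendar, scheduled marrows fall at the end of even cycles, so a rise seen only in marrow can wait 2 x 28 = 56 days for the next scheduled marrow. After a documented CR this is overridden, because the footnote requires a marrow when relapse is suspected. Once treatment stops, 7.4 specifies monthly response assessments only for responders. For a patient with stable disease, the one disease assessment specified is the end-of-treatment visit within 28 days of the last dose (7.3). A second assessment 28 days after the rise may therefore never be scheduled.

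**4. Size under the first reading.** Assumed inputs, not in the documents: constant hazard h; a share p of true first events are progressions; a fraction f of those switch before confirmation and are permanently censored at the rise.

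- Counted hazard = h x (1 - p x f)
- Median = ln 2 / [h x (1 - p x f)]
- Ratio to the true median = 1 / (1 - p x f)

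| p | f = 0.1 | f = 0.2 | f = 0.3 | f = 0.5 |
|---|---|---|---|---|
| 0.6 | 1.06 | 1.14 | 1.22 | 1.43 |
| 0.7 | 1.08 | 1.16 | 1.27 | 1.54 |
| 0.8 | 1.09 | 1.19 | 1.32 | 1.67 |

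For example, p = 0.7 and f = 0.5 gives 1 / (1 - 0.35) = 1.54.

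**5. Simulation check.** Kaplan-Meier on 8,000 simulated patients per setting, with p = 0.8, 28-day assessments and an assumed true median of 6 months (6.4 when rises are detected on that grid). For the second row, an assumed 3-month median from rise to death.

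| Handling of switchers | f = 0.1 | f = 0.3 | f = 0.5 |
|---|---|---|---|
| Censored at the rise | 7.3 | 8.3 | 11.0 |
| Followed to death, death counted | 6.4 | 7.4 | 8.3 |

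The 28-day grid makes small differences coarse. The direction agrees with the formula, and the shift is smaller, down to none at f = 0.1, when later deaths count.

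**6. DoR.** An unconfirmed rise is not an Appendix I relapse, so it does not end the response. DoR can then run to a later confirmation, to death or to the last clinical assessment, and may include time on the new therapy. This route differs from that in step 2.

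**The case against.** **The gap in 8.3 may not exist in practice.** Section 8.3 speaks of documented and reported progression, not confirmed progression, and study treatment stops on evidence of progression (5.6.1). If a site may report a single rise, the event falls on the right date. This stands as a possibility, but no section says so, and 9.3.2 points to criteria that require two assessments.

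**8.3 is not the only PFS rule.** Section 9.5 and the synopsis have no new-therapy censoring. This stands, and means the documents conflict. It does not repair the estimate, because the unconfirmed rise still does not count.

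**The last assessment need not be the rise.** An end-of-treatment disease assessment may come between the rise and new therapy, and after CR a marrow is required at suspected relapse. Both stand, so a 56-day wait cannot be claimed for every patient.

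**Switching may be uncommon.** Patients who still benefit may stay on treatment after progression (4.4, 5.6.1). The documents give no switching rate in either direction.

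**DoR.** A reader might infer that DoR is also censored on the date of the rise. The documents do not support this: the new-therapy sentence belongs to PFS, and responders who stop for other reasons are assessed monthly until relapse or death.

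**Nothing is tested.** PFS and DoR are descriptive Kaplan-Meier summaries. This stands and limits the consequence.

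**Conclusion.** The concern holds for PFS. Under 8.3 read with Appendix I, a patient who switches after a first qualifying rise can be censored on the date of that rise. The censoring is informative and the bias is upward, provided that the rise was true progression and that a single rise may not be reported as progression. The conflict between 8.3 and 9.5 with the synopsis, and the missing order of precedence when death follows new therapy, leave the handling of these patients undetermined.

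The size cannot be derived from the documents. The factors 1.08 to 1.54 (p = 0.7, f = 0.1 to 0.5) assume p, f, a constant hazard and permanent loss of each such event. It would be tempting to read 54% as the expected bias; it is only the upper end of that assumed range, and the shift is smaller if later deaths count.

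For DoR only the narrower point stands: an unconfirmed rise does not end response. No error rate, sample size or decision rule is affected.

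**What to change.** Change the protocol wording in 8.3, 9.5 and the synopsis so that all three carry one PFS rule:

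- An assessment that meets an Appendix I relapse or PD threshold is the event, on its own date, if new anti-leukaemic therapy starts before a confirmatory assessment.
- Confirmed events are dated to the first qualifying assessment.
- Censoring at new therapy applies only when the last assessment before it showed no relapse or PD.
- State which rule prevails when a patient starts new therapy and then dies.

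For DoR, apply the same event dating and censor at the last response assessment. Do not add new-therapy censoring that would conflict with the treatment-policy strategy for transplant in 8.2.5.

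Cost: a protocol wording change, with no added visits or patients. PFS and DoR become somewhat shorter, and a few rises that a second assessment might not have borne out will count as events. Reporting how many events rest on a single assessment would make that visible.
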